9.6.2 Safety Objectives

9.6.2.1 Analysis Set and Grouping for the Analyses

For all safety analyses, the safety set will be used.

The overall observation period will be divided into 3 mutually exclusive segments:

1. Pre-treatment period: from day of patient's informed consent to the day before first dose of study medication
2. On-treatment period: from day of first dose of study medication to 90 days after last dose of study medication
3. Post-treatment period: starting at Day 31 after last dose of study medication

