11. Change to exclusion criterion #19 and addition of Section 6.6 on contraception requirements (Section 5.3 and Section 6): Contraception requirement for women of child-bearing potential was changed to be consistent across IMCgp100 clinical trials and to be consistent with Clinical Trial Facilitation Group recommendations.
12. Update of exclusion criteria #7 and #8 to add testing for HIV and Hepatitis B and C as per local regulations (Section 5.3): Screening for HIV and Hepatitis B and C will be done if required by local regulations.
13. Addition of Section 2.4 regarding the overall benefit-risk assessment
14. Inclusion of Table 7-3 to clarify frequency of vital signs.
15. Modification of Section 11.3 to harmonize the informed consent procedures with inclusion criterion #2 and clarify the informed consent process.
16. Increased duration of safety follow up period (Sections 3.3, 7.2.3, 7.2.5, 8.1, 8.5, 9.1, & 9.6.2.1 as well as Table 7.1) to provide further safety information and be consistent across IMCgp100 clinical trials
17. Clerical Changes are made throughout the protocol to improve clarity.

Institutional Review Board/Independent Ethics Committee

A copy of this amended protocol will be sent to the Institutional Review Board (IRB) or Independent Ethics Committee (IEC) and Health Authorities. The changes described in this amended protocol require IRB or IEC approval. Changes herein affect the Informed Consent, and sites are required to update and submit for approval a revised Informed Consent that takes into account the changes described in this amended protocol. The revised ICF will replace the previous ICF.

7.0 DE Local Amendment 1

Amendment Rationale

This amendment updates the contraception requirement for women of child-bearing potential to be consistent across IMCgp100 clinical trials and to be consistent with Clinical Trial Facilitation Group recommendations.

Testing of all patients for HIV and hepatitis B and C infections is added if required by local regulations.

An overall benefit-risk assessment has been added to the protocol rationale.

Changes to the Protocol

1. Change to exclusion criterion #19 and addition of Section 6.6 on contraception regulations (Section 5.3 and Section 6)
2. Update of exclusion criteria #7 and #8 to add testing for HIV and hepatitis B and C as per local regulations (Section 5.3)
3. Addition of Section 2.4 regarding the overall benefit-risk assessment

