3 STUDY DESIGN

3.1 Description of Study Design and Populations

This is a Phase 1/2 study of IMCgp100 administered on a QW basis with an intra-patient escalation dosing regimen. The intra-patient escalation occurs at the third weekly dose on C1D15. According to this regimen, all patients in the trial will receive 2 QW doses of IMCgp100 at a dose level below the identified RP2D-QW, and then a dose escalation will commence at the third weekly dose at C1D15 with the goal to achieve a long-term dosing regimen at a dose higher than that identified for the straight QW dosing regimen (RP2D-QW). The dose escalation will identify the RP2D-IE. (Intra-patient dose escalation regimen schematic, see Figure 3-1).

Phase 1: Dose Escalation

Phase 2: Expansion

Enrollment into the Phase 1 dose escalation portion has been completed and RP2D-IE was determined to be 68 mcg.

Figure 3-1 Intra-patient Escalation Regimen

In this dosing regimen, at C1D1 and C1D8, patients will all receive single-agent IMCgp100 at a dose below the 2RP2D-QW of 50 mcg. Patients will receive 20 mcg IMCgp100 on C1D1 and 30 mcg IMCgp100 on C1D8. The intra-patient escalated dose will then commence at C1D15 and will continue at that same escalated dose level thereafter.

The Phase 1 portion of the study will be a standard 3+3 dose escalation design. Dose cohort levels are presented in [Table 6-2](#). After the dose escalation portion is complete and the MTD or the RP2D-IE is identified, the Phase 2 expansion cohorts in mUM will be enrolled. The Phase 2 expansion Cohort A will enroll patients with mUM in the second-line setting after disease progression following systemic

treatment with a checkpoint inhibitor and will recruit approximately 20 patients. The Phase 2 expansion Cohort B will enroll patients with mUM in the second/third-line setting with up to one prior line of LDT and will recruit approximately 130 patients. A total of approximately 150 patients will be enrolled into the Phase 2 expansion phase of the study. See Figure 3-2.

[figure not shown]

Figure 3-2 Study Design

LDT = liver-directed therapy; ORR = objective response rate; RP2D = recommended Phase 2 dose; RP2D-IE = recommended Phase 2 dose — intra-patient escalation.

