8 ADVERSE EVENTS AND SAFETY REPORTING

8.1 Assessment of Safety

All patients who receive any treatment with IMCgp100 will be considered evaluable for safety. All AE regardless of study drug relationship will be collected up to the 90-day follow-up.

Timely, accurate, and complete reporting and analysis of safety information from clinical studies are crucial for the protection of patients and is mandated by regulatory agencies worldwide. The Sponsor and CRO have established standard operating procedures in conformity with regulatory requirements worldwide to ensure appropriate reporting of all safety information; all clinical studies conducted by the Sponsor or its affiliates will be conducted in accordance with those procedures.

Individual AEs should be evaluated by the investigator and should be reported to the CRO/Sponsor for evaluation. This includes the evaluation of the event's seriousness and the causality between the investigational medicinal product(s) and/or concomitant therapy and the AE. The CRO/Sponsor is required to maintain detailed records of all AEs reported by the investigator(s) and to perform an evaluation with respect to seriousness, causality, and expectedness. On request of a competent authority in whose territory the clinical trial is being conducted, the sponsor should submit detailed records of all AEs which are reported to him by the relevant investigators. Case report processing concerns evaluation of data in individual cases, identification of individual cases requiring specific handling, recognition and processing of alerts, and any other data processing of aggregated cases.

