9.6.2.2 Adverse Events

Summary tables for AEs include only AEs that are new or worsened during the on-treatment period (treatment-emergent AEs). However, all safety data (including those from the pre- and post-treatment periods) will be listed and those collected during the pre-treatment and post-treatment period are to be flagged.

The incidence of treatment-emergent AEs will be summarized by system organ class and/or preferred term, severity (based on NCI CTCAE v.4.03 grades), type of AE, and relation to study treatment by treatment group. Deaths reportable as SAEs and non-fatal SAEs will be listed by patient and tabulated by type of AE and treatment group.

Definitions of notably abnormal vital signs results (e.g., hypotension) will be specified in the SAP and a shift table baseline to worst on-treatment result will be produced by the Phase 1 dose escalation and Phase 2 dose expansion groups.

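### One 90-day treatment-emergent window covers patients followed under two safety follow-up lengths, and days 31–90 after last dose fall in two periods called mutually exclusive

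*Protocol*

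**What the plan says.** Section 9.6.2.1 introduces the safety periods with "The overall observation period will be divided into 3 mutually exclusive segments". The second segment is "On-treatment period: from day of first dose of study medication to 90 days after last dose of study medication" and the third is "Post-treatment period: starting at Day 31 after last dose of study medication". Neither is split by phase or by protocol version.

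Section 9.6.2.2 makes the second segment decisive for the tables: "Summary tables for AEs include only AEs that are new or worsened during the on-treatment period (treatment-emergent AEs". Incidence is shown by treatment group. Other safety data are listed, and "those collected during the pre-treatment and post-treatment period are to be flagged".

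Collection under the current text matches the 90 days. Section 8.1 says "All AE regardless of study drug relationship will be collected up to the 90-day follow-up", and Sections 3.3, 7.2.3 and 8.5 agree.

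The 90 days were not always the rule. Item 16 of the Amendment 7 changes reads "Increased duration of safety follow up period" and lists Section 9.6.2.1 among the sections altered. By then Phase 1 accrual was over, as Section 3.1 states: "Enrollment into the Phase 1 dose escalation portion has been completed and RP2D-IE was determined to be 68 mcg". The expansion cohorts had been set up under earlier amendments, and the Amendment 7 log describes the expansion as enrolling.

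**The concern.** A patient who stopped drug and completed AE collection under the earlier rule was not asked about events for the full 90 days. The treatment-emergent tables still give that patient a 90-day window. In a crude incidence table the uncollected days look the same as days without an event.

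Where two columns hold different shares of such patients, a difference in late AE or SAE incidence is partly a product of the protocol version. Phase 1 beside Phase 2 is the obvious case. Early and late enrollees inside the 68 mcg expansion are another, where pooling understates late events.

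The boundary error compounds this. An event on, say, day 45 after last dose is tabulated as treatment-emergent under one line of the list and flagged as post-treatment under the next, so two programmers could produce different tables from the same text. The two problems are also linked. If the boundary is taken at day 30, late events leave the tables. If it is taken at day 90, unequal ascertainment enters them.

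**Working it through.** The plan prints no figure on this point, so there is none to reproduce.

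**1. Overlap of the periods (no assumption).** On-treatment ends on day 90 after last dose and post-treatment starts on day 31, both from Section 9.6.2.1. Days in both: 90 − 31 + 1 = 60, that is days 31 to 90. The segments are therefore not mutually exclusive.

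**2. Could patients have finished under the earlier rule?**
- Amendment 5 is dated 11 April 2017 and already names the recommended Phase 2 dose.
- Amendment 6, which turned the expansion into formal Phase 2 testing, is dated 15 December 2017.
- The latest date found in the current text is a web access date of 18 October 2018 in the reference list, so this version is no older than that.
- Intervals: 11 April 2017 to 18 October 2018 is 555 days; 15 December 2017 to 18 October 2018 is 307 days.
- Section 1.1 puts median survival in metastatic disease below 12 months.

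It is a fair inference, not a printed fact, that a good number of Phase 1 patients and some expansion patients ended AE collection before Amendment 7. The number cannot be derived. Section 9.1 expects some Phase 1 patients to remain on treatment after the Phase 1 data cut-off, and anyone still dosing when the amendment took effect gets the full 90 days.

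**3. Share of the window unobserved (assumption: earlier length 30 days, suggested only by the leftover Day 31).** Observed: 30/90 = 33%. Unobserved: 60/90 = 67%.

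**4. Illustration of the effect on a crude rate.** Let p be the incidence of a given event up to last dose and h the hazard per 30 days afterwards, both assumed. Incidence with m blocks of 30 days observed is 1 − (1 − p)·exp(−h·m). The gap between a 90-day (m = 3) and a 30-day (m = 1) window is (1 − p)·[exp(−h) − exp(−3h)].

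| p | gap at h = 1% | gap at h = 10% |
|---|---|---|
| 5% | 7.8% − 5.9% = 1.9 points | 29.6% − 14.0% = 15.6 points |
| 50% | 51.5% − 50.5% = 1.0 point | 63.0% − 54.8% = 8.2 points |
| 90% | 90.3% − 90.1% = 0.2 points | 92.6% − 91.0% = 1.6 points |

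These gaps compare a group wholly under the earlier rule with one wholly under the current rule. If only a fraction f of a group finished under the earlier rule, the gap is f times as large. The table shows the direction and which events are exposed; it does not estimate what happened in this trial.

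**The case against.** A reader might infer that the Phase 1 dose cohorts cannot be compared with one another. The document does not support that. All of them were enrolled before Amendment 7 and so largely share one era, and Phase 2 uses a single regimen. The contrast lies between Phase 1 and later Phase 2 patients, and within the expansion.

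A reader might also infer that all Phase 1 and early Phase 2 patients were followed for less time, or that the gap is tens of percentage points. Neither is printed. Section 3.1 says that enrolment, not treatment, was complete. Only patients whose collection ended before the amendment are affected, and any point estimate of the gap depends wholly on assumed hazards.

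The displays are descriptive: no test between phases or doses on AE incidence is stated. The synopsis says dose-limiting toxicity in the first-in-human study was confined to the first two weeks of dosing, and Section 6.9.2 places the usual onset of cytokine release syndrome within hours of the first three doses. A patient already counted for an event adds nothing later, so common early toxicities barely move. All of this stands and limits the point to late or uncommon events.

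It can also be said that patients followed under earlier protocol versions are ordinary SAP material. For the added table that is partly right, and the SAP is a suitable home for it. But Section 9.6.2.1 fixes the window and both boundaries itself, and the contradiction lies in that text.

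Finally, cutting the main tables back to the shorter window would push aside data that Amendment 7 set out to collect, and restricting a 90-day table by date of last dose would select the longest-treated of the early enrollees. Both objections are sound, and the fix avoids both.

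**Conclusion.** Two things hold. First, Section 9.6.2.1 contradicts itself: 60 days after last dose belong to two periods said not to overlap. This rests on the printed text alone. Second, the single 90-day treatment-emergent window is applied without provision for patients whose AE collection ended under the earlier, shorter follow-up, so part of their window is very likely counted as event-free. This rests on the amendment log for the lengthening and on the dates for the inference that such patients exist. The log is used only as evidence that follow-up differed between patients, not as text conflicting with the current version.

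The size is not computable. The 67% unobserved share needs the 30-day assumption, and the 0.2 to 15.6 point illustration needs assumed hazards as well. The primary response endpoint is untouched. The consequence is confined to how late or uncommon AEs and SAEs read across phases and within the 68 mcg expansion. That merits correction because it is cheap and because the safety tables cannot be programmed unambiguously as the text stands.

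**What to change.** - In Section 9.6.2.1, start the post-treatment period on the day after the on-treatment period ends: Day 91 if the 90-day window is kept.
- Keep the 90-day treatment-emergent table as the main table, and state with it, by phase, how many patients had AE collection end under the earlier rule and what that earlier length was.
- In Section 9.6.2.2 or the SAP, add one treatment-emergent AE/SAE table on the post-dose window collected in all patients, and use it for any side-by-side display of Phase 1 and Phase 2.

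The cost is a few lines of wording and one extra table. The common-window table will show fewer late events than the main one, so the two need clear labels.

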9.6.2.2 Adverse Events

Summary tables for AEs include only AEs that are new or worsened during the on-treatment period (treatment-emergent AEs). However, all safety data (including those from the pre- and post-treatment periods) will be listed and those collected during the pre-treatment and post-treatment period are to be flagged.

The incidence of treatment-emergent AEs will be summarized by system organ class and/or preferred term, severity (based on NCI CTCAE v.4.03 grades), type of AE, and relation to study treatment by treatment group. Deaths reportable as SAEs and non-fatal SAEs will be listed by patient and tabulated by type of AE and treatment group.

Definitions of notably abnormal vital signs results (e.g., hypotension) will be specified in the SAP and a shift table baseline to worst on-treatment result will be produced by the Phase 1 dose escalation and Phase 2 dose expansion groups.

9.6.2.3 Laboratory Abnormalities

For laboratory tests covered by the NCI CTCAE version 4.03 the study team will grade laboratory data accordingly. For laboratory tests covered by NCI CTCAE, a grade 0 will be assigned for all non-missing values not graded as 1 or higher. For laboratory tests where grades are not defined by CTCAE, results will be graded by the low/normal/high classifications based on laboratory normal ranges.

The following by-treatment summaries will be generated separately for hematology, biochemistry, and other laboratories:

- Frequency table for newly occurring on-treatment grades 3 or 4 and all grades
- Shift tables of laboratory and ECG data using CTCAE grades to compare Baseline to the worst on-treatment value
- Listing of all clinically relevant laboratory data and relevant ECG data with values flagged to show the corresponding CTCAE grades and the classifications relative to the laboratory normal ranges

9.6.2.4 Other Safety Variables

- Vital signs absolute values and changes from Baseline will be summarized. Normal ranges will be specified in the SAP and shift tables of Baseline to worst on-treatment results will be produced
- ECG data: QTc interval absolute values and changes from Baseline will be summarized. Abnormalities will be classified according to NCI CTCAE grades and shift tables of Baseline to worst on-treatment results will be presented
- Physical examination data will be listed and abnormalities will be flagged

9.6.2.5 Tolerability

Tolerability of study treatment will be assessed by summarizing the number of treatment dose interruptions and dose reductions. Reasons for dose interruptions and dose reductions will be listed by patient and summarized.

9.6.2.6 Pharmacokinetics

The PK parameters that will be assessed are presented in [Table 9-1](#).

Table 9-1 Pharmacokinetic Parameters to be Analyzed

AUC _{last}	The area under the curve (AUC) from time 0 to the last measurable concentration sampling time (t _{last}) (mass x time x volume-1)
AUC _{inf}	The AUC from time 0 to infinity (mass x time x volume-1)
C _{max}	The maximum (peak) observed plasma, blood, serum, or other body fluid drug concentration after single dose administration (mass x volume-1)
T _{max}	The time to reach maximum (peak) plasma, blood, serum, or other body fluid drug concentration after single dose administration (time)
T _{1/2}	The elimination half-life associated with the terminal slope (λz) of a semi logarithmic concentration-time curve (time). Use qualifier for other half-lives
CL	The total body clearance of drug from the plasma (volume x time-1)
V _z	The apparent volume of distribution during terminal phase (associated with λz) (volume)
AR	Accumulation Ratio=C _{max} (multiple dose)/C _{max} (single dose)

The safety set will be used in all PK data analysis and PK summary statistics.

Pharmacokinetic Analyses

Descriptive statistics of all PK parameters for IMCgp100 will include arithmetic and geometric mean, median, stable disease, and coefficient of variation, geometric coefficient of variation, and minimum and maximum. Zero concentrations will not be included in the geometric mean calculation. Since T_{max} is generally evaluated by a non-parametric method, median values and ranges will be given for this parameter. Missing concentration values will be reported as is in data listings. Concentration values below lower limit of quantitation will be handled as 0 in summary statistics, and reported as is in data listings. Any missing PK parameter data will not be imputed.

Further analyses may be conducted using population PK approaches. In addition, a model based approach may be used to explore the potential relationship between efficacy, safety, and/or biomarker endpoints and IMCgp100 concentration and/or exposure metrics. All analyses will be reported either in the clinical study report or a stand-alone report.

The concentration-/AE-immunogenicity relationship will be explored graphically and tabulated to characterize a relationship between the changes from screening immunogenicity presence and serum concentration of IMCgp100. Further details will be described in the SAP.

9.7 Exploratory Analyses

9.7.1 [REDACTED]

[REDACTED]

[REDACTED]

9.7.1.2 [REDACTED]

[REDACTED]

[REDACTED]

[REDACTED]

[REDACTED]

[REDACTED]

[REDACTED]

[REDACTED]

9.8 Interim Analysis

For the Phase 1 cohorts, the dose-escalation design foresees that decisions based on the current data are taken before the end of the study. More precisely, after each cohort in the dose escalation part, the next dose will be chosen depending on the observed data (based on safety, tolerability, PK, pharmacodynamic, and efficacy data, and recommendations from participating investigators). Details of this procedure and the process for communication with investigators are provided in [Section 6.3.3](#).

For the Phase 2 expansion (approximately n=150), an IDMC will review the safety data on an ongoing basis. In addition, a benefit-risk assessment involving review of efficacy and safety data will take place once approximately 75 evaluable patients have been treated/followed for at least six months. The primary endpoint of ORR, as assessed by the ICR, will be summarised with 95% confidence intervals (Clopper Pearson method). ORR based on the local radiological assessment will be summarised as a sensitivity analysis. Duration of response and other secondary efficacy endpoints will be described. Further details will be provided in the SAP.

9.9 Independent Data Monitoring Committee

An IDMC will be established to provide oversight of safety and efficacy considerations in the Phase 2 expansion portion of this study. The IDMC will act in an advisory capacity and make recommendations regarding steps to ensure both subject safety and the ethical integrity of the trial. The voting members of the committee are external to Immunocore, and will not otherwise be involved with the trial. The IDMC will include 3 clinicians experienced in oncology/melanoma and 1 statistician. Specific details regarding IDMC responsibilities, governance, and documentation will be described in a separate charter that is reviewed and approved by the IDMC members. Immunocore has primary responsibility for design and conduct of the study.

The IDMC will monitor trial safety approximately every 4 months, or at a frequency described in the IDMC charter. In addition, they will perform a benefit-risk assessment by reviewing both efficacy and safety data after approximately 75 evaluable patients in the expansion phase have been treated/followed for at least 6 months.

Following each IDMC meeting, the IDMC will provide recommendations to the Sponsor on any changes that may be needed to the future conduct of the study or if the study should continue as planned.

